1.2 Rationale

1.2.1 Hypothesis and Experimental Aspects of the Clinical Trial

Long-term data of the clinical trial [10] suggest that more than 50% of the patients with R-only, but only a small percentage of RL patients needed treatment beyond 2 years. In fact, in 9/10 patients of experimental group (R+L) treatment was stopped after only 11 months without relapse. The reduction of re-treatments would decrease the burden of treatment for the single patient. Furthermore, improved final visual acuity is expected in patients undergoing the laser treatment, which may preserve the reading/ driving ability and improve the quality of life (QoL) compared to the R-only arm. This forms the rationale for the planned study in which the hypothesis will be tested.

Intravitreal injection of Ranibizumab will be applied in all patients in the CoRaLa II trial (chap.6.3). The experimental group receives additional targeted laser photocoagulation of the peripheral areas of capillary non-perfusion (up to 4 laser treatments if indicated within 1st year of the study). No further additional treatments in study eye will be given in any of the arms of the trial.

To assess a treatment success meaning the time point when 6 months without any further need of injections is stated (based on the predefined criteria) all patients will be seen monthly at the trial site during the first year.

In patients with treatment success within the first trial year, these patients will be followed at "mandatory visits" only.

In the second year, patients who are free of intravitreal treatment \geq 2 months will be seen bi-monthly. If the treatment interval is $<$ 2 months, the patients will be followed monthly until the treatment success has been reached or treatment interval is \geq 2 months for at least 2 consecutive injections.

After stating success of treatment (treatment-free interval \geq 6 months) all patients will be seen at all "mandatory visits" later on in the course of trial. These visits are planned at month 16, 20, 24 and 29. For all patients without earlier "success" last possible Ranibizumab injection within the trial is at month 23 (End of treatment; EoT). Patients, who required further treatment will be treated after month 23 out of trial. All patients will be asked to come for the observational visit at month 29 to assess visual acuity, retinal thickness, the (latest) success possible, and to document the potential late relapses of the edema, which required the treatment out of the trial.

1.3 Risk-Benefit Considerations

The treatment with Ranibizumab in the control group, as well as in the experimental *group* are standard therapies, described in German treatment strategies [5]. Standard care will follow defined re-treatment criteria for Ranibizumab injections according to guidelines [1].

Laser photocoagulation of the retina is well established treatment technique for ischemic retinal disorders as diabetic retinopathy or retinal vein occlusions. Since decades, panretinal (scatter) laser photocoagulation is used for treatment of the neovascular complications as e.g. vitreous bleeding, neovascular glaucoma or tractive retinal detachment. However, the Central Vein Occlusion Study Group did not find any significant benefit of profilactic panretinal (non-selective) scatter laser photocoagulation in patients with ischemic CRVO [24]. This study focused on ischemic cases only, which have a poor natural prognosis and did not evaluate the visual acuity. Therefore, the implication of these results for current treatment strategy is strongly limited.

Since no established evidence exists on potential benefits of laser therapy as add-on-treatment to usual care (Ranibizumab injections) randomized treatment allocation appears justified.

Intravitreal (IVT) injection of Ranibizumab used in this study will be given according to the label and follow the German treatment strategies [5]. The most serious possible risks of IVT are endophthalmitis and retinal detachment.

The possible risks and side events after retinal laser photocoagulation are the local pain, and temporary increased intraocular pressure. Late side effect of this treatment may be defects in the visual field. In the CoRaLa II trial, the laser photocoagulation will be performed targeted in non-perfused retinal areas only and therefore it is not expected that significant defects of visual field will occur. However, the visual field will be evaluated at the beginning of maintenance phase at month 4 and at end of study to confirm this expectation.

It is expected that the total amount of required IVT can be reduced in the experimental group (combined treatment Ranibizumab and selective laser) compared with controls (Ranibizumab only).

Patients who develop neovascularization of the retina or in the anterior segment (rubeosis iridis) will be withdrawn from the study and receive a rescue panretinal laser photocoagulation (PRP) as a full scatter.

2 Objectives

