Safety visit and end of (S)AE report period (4 weeks after EoT) for patients who still need monthly intravitreal injections (no success reached).

- Blood pressure and pulse
- QoL (Visual Function Questionnaire) before the ophthalmologic investigation will be performed
- Documentation of Adverse events, critical ocular events and Concomitant medication
- Ocular assessment (assess prior to injection, assess in the study eye only, see exceptions in text below):
 - Investigation of BCVA using ETDRS chart **performed by a blinded assessor in both eyes!**
 - IOP
 - Gonioscopy
 - Slit lamp biomicroscopy
 - Visual field performed **in both eyes!**
 - OCT **in both eyes!** (in addition OCT will be evaluated by the CoRaLa II Central Reading Center)
 - OCT-Angiography **in both eyes!** (in addition OCT-Angiography will be evaluated by the CoRaLa II Central Reading Center)
 - Ophthalmoscopy performed **in both eyes!**

- Fundus photography and Fluorescein angiography (FAG) **in both eyes!** performed according to the imaging protocol and evaluated by the CoRaLa II Central Reading Center.
- Documentation if an injection with Ranibizumab was needed. (Injections of Ranibizumab after Months 23 are no longer documented as study treatment.)

6.4 Follow-up Visit 25 (month 29 +/- 7 days) **EoS** is a mandatory visit for all patients

Ocular assessment (study eye only) providing the final assessment of all secondary endpoints and any potentially late occurrence of critical ocular events.

- Blood pressure and pulse
- Critical ocular events and Concomitant medication
- Ocular assessments in study eye only:
 - Investigation of BCVA using ETDRS chart **performed by a blinded assessor**
 - IOP
 - Slit lamp biomicroscopy
 - OCT (in addition OCT will be evaluated by the CoRaLa II Central Reading Center)
 - OCT-Angiography (in addition OCT-angiography will be evaluated by the CoRaLa II Central Reading Center)
 - Ophthalmoscopy
- Documentation how many injections with Ranibizumab were needed. (Injections of Ranibizumab after Months 23 are no longer documented as study treatment.)

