6.5 Premature Termination of the Therapy and Follow-up for Individual Patients

6.5.1 Premature Termination of the Therapy for Individual Patients

Each premature termination of the trial therapy has to be documented by the responsible investigator. If possible, date, circumstances of and reason for the termination should be documented in detail and communicated to the ZKS Leipzig Data Management. Premature termination should be avoided.

The premature termination of trial therapy for an individual patient may be considered for the following aspects:

- progress of neovascular complication (Increase of NVE's or NVD's, neovascular glaucoma) (see rescue treatment)
- persisting macular edema without response to Ranibizumab
- protocol violations if they indicate a significant risk to the patient's safety
- non-compliance
- pregnancy

- at the discretion of the investigator
- for reasons of medical prudence based on DSMB recommendations or
- withdrawal of consent

All patients with premature therapy termination (except in case of consent withdrawal) will, however, be instructed to return for a safety follow-up visit 4 weeks after last study treatment. Further, all patients (except in case of consent withdrawal) will be offered the visit in Month 29, because at this visit the primary endpoint is documented as well as the major secondary endpoints.

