6.5.2 Rescue Treatment

Patients with progress of neovascular complication (Increase of NVE's or NVD's, neovascular glaucoma) will receive rescue treatment with pan-retinal photocoagulation (PRP) outside the study intervention.

Patients with persisting macular edema without response to Ranibizumab will be treated with intravitreal Aflibercept (Eylea) or dexamethasone implant (Ozurdex) out of the study.

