⇒ **Defects of peripheral Visual fields (VF – complementary outcome)**

The visual field defects will be captured by assessing the retinal sensitivities of various points in the mid-peripheral and peripheral visual fields at month 4 and 24 in both eyes. Eyes with excessive false positive response or excessive fixation loss will be excluded from analysis.

A false positive response is defined as a response to a false positive test, i.e. a projector movement (or other external stimulus) when no stimulus is presented. Excessive false positive response is defined as [(# false positive responses) ÷ (# false positive tests)] *100 >33%.

A fixation loss is defined as a response to a fixation loss test, i.e. a stimulus presented to the blind spot. Excessive fixation loss was defined as [(# fixation losses) ÷ (# fixation loss tests)]*100 > 33%. Outlying values will be truncated at ±3 standard deviation from the mean to minimize the effect of potential outliers.

⇒ **Number of Ranibizumab injections**

All patients will receive 3 intraocular injections. The application of further injections is guided by standardized retreatment criteria. The number of injections required will be recorded for every patient.

⇒ **The progression to neovascularization of the retina or anterior segment**

Patients will be evaluated for the development of neovascularization of the iridocorneal angle by gonioscopy in conjunction with slit lamp biomicroscopy at screening visit and further at month 12 and 24. The examination should be performed after OCT and before funduscopy, fundus photography, and fluorescein angiography.

All patients will be investigated for the development of neovascularization of the optic disc or of the retina elsewhere by ophthalmoscopy in mydriasis at every visit. The presence of neovascularization will be documented by fundus photography. If suspected lesion could not be surely distinguished between neovascularization or shunt vessels by ophthalmoscopy, a fluorescein angiography will be performed.

Patients in whom a neovascularization will be found will undergo panretinal scatter laser photocoagulation as a rescue treatment according the recommendations of CRVO study group [24].

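### Section 1.3 withdraws patients who develop neovascularization from the study, whereas section 6.5.1 stops only trial therapy and keeps the month-29 visit

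*Protocol*

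**What the plan says.** Section 1.3 closes the risk-benefit discussion with a rule. Patients who develop neovascularization of the retina or the anterior segment "will be withdrawn from the study and receive a rescue panretinal laser photocoagulation".

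Section 6.5.1 handles the same situation differently. "The premature termination of trial therapy for an individual patient may be considered for the following aspects", it says, and its list includes "progress of neovascular complication", explained as an increase of retinal or disc neovascularization or as neovascular glaucoma. Patients who stop therapy early return for a safety visit 4 weeks after the last study treatment, and "all patients (except in case of consent withdrawal) will be offered the visit in Month 29". The reason given is that the primary and major secondary endpoints are documented there.

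Two further sections cover the rescue laser:
- Section 6.5.2: patients with progression "will receive rescue treatment with pan-retinal photocoagulation (PRP) outside the study intervention". Leaving the study is not mentioned.
- Section 7: "Patients in whom a neovascularization will be found will undergo panretinal scatter laser photocoagulation as a rescue treatment". Leaving the study is again not mentioned.

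Month 29 is planned for everyone. Section 1.2.1 states "All patients will be asked to come for the observational visit at month 29", the heading of section 6.4 says that this visit "is a mandatory visit for all patients", and section 9.1 plans 29 months of follow-up for all patients.

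**The concern.** Leaving the study and stopping trial therapy have different consequences for the data. A patient who has left the study has no month-29 visit. Several planned items end with it:

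- **Visual acuity and central subfield thickness at month 29.** Section 9.5.2 names the treatment-by-visit interaction at this visit as the contrast of interest.
- **The injection count to month 29**, a secondary endpoint in section 9.2.2.
- **Critical ocular events after withdrawal.** Section 2.2 promises them to the end of the study, but section 8.1.5 records them only while the patient participates.
- **Primary-endpoint follow-up.** Under section 9.2.1, drop-outs without earlier success are censored when their observation ends.

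The affected patients are not a random subset. They are selected by neovascularization, an outcome compared between arms (sections 6.3 and 9.5.2) that laser treatment may influence. The mixed model for acuity and thickness assumes data missing at random given its terms, and neovascularization is not one of them.

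**Working it through.** **1. The texts side by side**

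| | 1.3 | 6.5.1 | 6.5.2 | 7 |
|---|---|---|---|---|
| Trigger | develops | progress / increase | progress / increase | found |
| Force | will | may be considered | will (rescue laser) | will (rescue laser) |
| What ends | the study | trial therapy | not stated | not stated |
| Month 29 | not mentioned | offered | not mentioned | not mentioned |

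Sections 1.3 and 6.5.1 differ on trigger, force and what ends. The triggers agree only if a first occurrence is read as an increase.

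**2. The plan's own sample size**, needed for the power check. Inputs from section 9.4: 50% (ranibizumab alone) and 20% (with laser) at two years, read as still without success; two-sided 5%; 90% power.
- Hazard ratio = ln 0.5 / ln 0.2 = 0.431, or 1/0.431 = 2.32 for success with laser.
- Events (Schoenfeld) = 4 × (1.960 + 1.282)² / (ln 0.431)² ≈ 59.2, rounded up to 60.
- Mean event probability = (0.50 + 0.80)/2 = 0.65, and 60/0.65 = 92.3. The stated 92 is reproduced.
- At N = 110: 110 × 0.65 = 71.5 events, power 94.5%.

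**3. Patients losing month 29 if 1.3 is followed.** The protocol gives no neovascularization rate, so 5-20% per arm is an assumption. With 1:1 allocation there are 55 per arm.
- 0.05 × 55 = 2.75 and 0.20 × 55 = 11, so about 3-11 per arm.
- Standard error of the month-29 mean: 1/√0.95 = 1.026 and 1/√0.80 = 1.118, so 3-12% larger. This is an upper bound, because it ignores what earlier visits contribute through the model.

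**4. Eyes with no post-baseline value in the acuity and thickness model**, which uses baseline and months 12, 16, 20, 24 and 29. These are the eyes withdrawn before month 12.
- Onset uniform over months 2-29: 10/27 × (2.75 to 11) = 1.0 to 4.1 per arm.
- Onset uniform over months 2-24: 10/22 × (2.75 to 11) = 1.25 to 5.0.
- Worst case, all onsets in months 3-12: 2.75 to 11.

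**5. Primary endpoint.** This was simulated with 400,000 patients per arm, exponential time to success (50% and 80% at 24 months) and administrative censoring at 24 months. Onset was uniform over months 2-24 with no success afterwards, which is a severe assumption.

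| Rate, ranibizumab alone / with laser | HR if censored | HR if followed |
|---|---|---|
| 5% / 5% | 2.32 | 2.30 |
| 20% / 20% | 2.32 | 2.26 |
| 15% / 5% | 2.32 | 2.41 |
| 20% / 5% | 2.33 | 2.48 |
| 5% / 15% | 2.32 | 2.17 |

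At rates of 5-20%, censoring overstates 24-month success by 1.0-4.0 points (ranibizumab alone) and 1.3-5.2 points (with laser). If the success hazard is only halved after onset, the overstatement is 0.4-1.9 points. If it is unchanged, there is none.

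**6. Power.** Log-rank test, 55 per arm, 4,000 runs: 94-95% without withdrawal and 92-93% when 20% of both arms are withdrawn.

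The simulation leaves out the 6-month treatment-free window that defines success, so its decimals are only illustrative.

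**The case against.** The best defence is that chapter 6.5 governs. Section 6.2.1 names it for procedures after a single patient's premature trial termination, and section 5.3.4 refers to it for patients switched to another drug. A patient withdrawn during treatment has necessarily ended therapy early, so 6.5.1 covers that patient, with consent withdrawal as its only exception. The protocol also describes treatment as out of the trial or study while follow-up continues (sections 1.2.1 and 6.5.2). Section 1.3 is a rationale section that prescribes no visits. The losses need a site to act on it against 6.5.1, 6.4 and 9.1.

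Most of this stands. It makes 6.5 the likely working text and the harm conditional. It does not remove the contradiction. The reference in 6.2.1 sits under eligibility violations, 1.3 itself points nowhere, and its wording is mandatory and names the study rather than the therapy. A site that regards a patient as withdrawn has no reason to offer month 29.

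The numbers also favour the defence. The worst case of 11 of 55 equals the 20% drop-out that section 9.4 plans for, and the mixed model uses incomplete patients.

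**Conclusion.** The contradiction is real and worth correcting, but its consequences are limited. If a site follows 1.3, and if neovascularization occurs in 5-20% of patients, about 3-11 of 55 per arm lose month 29. The cost falls mainly on the month-29 secondary endpoints and on later safety data in these eyes. The primary hazard ratio moves little, in a direction that depends on the rates by arm, and power stays above the required 90%.

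A reader might infer three stronger points that the protocol does not support:
- **That the plan discards month 29 for every patient with neovascularization, with nothing to show which section prevails.** Section 6.5.1 offers the visit, and 6.2.1 points to chapter 6.5.
- **That the primary analysis is materially biased.** The larger shifts need assumed imbalances between arms and no success after onset.
- **That the neovascularization rate is lost.** Section 6.3 counts a single occurrence, so these patients are already counted when they are withdrawn.

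**What to change.** In section 1.3, replace withdrawal from the study with: *withdrawn from trial therapy, receive rescue PRP outside the study intervention, and remain in follow-up as in 6.5.1 (4-week safety visit and month 29) unless consent is withdrawn.*

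In sections 6.5.1 and 6.5.2, word the trigger as *new occurrence or increase of neovascularization*, so that it matches 1.3 and section 7. In the same edit the clinical team should settle whether stopping therapy is then mandatory or optional.

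The amendment need not require all mandatory visits after therapy stops. A patient stopping after month 3 would face 13 of them (months 4-12 give 9, plus 16, 20, 24 and 29), which departs from what 6.5.1 chose. How rescue photocoagulation is handled in the analysis can be left to the SAP. The visits cannot, because an SAP cannot recover assessments that were never made.

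The cost is a wording amendment and the two visits already provided for in 6.5.1.

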2.1 Primary Objective

The primary objective is to evaluate whether or not the duration of guideline-conform [1] periodic ranibizumab injections may be shortened or even be successfully terminated in

patients with macular edema due to central retinal vein occlusion if early targeted peripheral laser photocoagulation is applied in parallel.

2.2 Secondary Objectives

Secondary objectives are to evaluate the visual acuity during and after the course of intervention, quality of life associated aspects and possible problems which might possibly be associated with the trial's intervention.

Secondary endpoints (sEP) are:

- the best corrected visual acuity (BCVA)
- central subfield thickness (CST)
- the number of ranibizumab injections required until treatment success and up to the end of observation.

Complementary outcomes of interest are:

- the proportion of subjects developing neovascularization(s) over total observation period.
- health-related quality of life (HrQoL)
- the area of non-perfusion
- vessel density & areal of foveal avascular zone
- potential visual field loss
- development of collaterals
- the number of laser treatments and the laser spots given in the experimental group (RL-arm)

Furthermore, the safety profile of the combined intervention will be compared to that of the guideline-based standard intervention in terms of (S)AEs/(S)ARs occurrence until 4 weeks after the last trial-related intervention. Critical ocular events will be evaluated until the end of study.

3 Trial design and description

3.1 Trial Design

The trial is a multi-centric, prospective, randomized, interventional, clinical trial with two parallel groups, phase IIIb and randomisation ratio of 1:1. Basic treatment for all patients (of control/R-only and experimental/ RL group) consists of three monthly intravitreal injections (0.5 mg Ranibizumab). Thereafter, up to 20 further injections if indicated by pre-defined criteria (in pro re nata (PRN) regimen as described in chapter 6.3 "Description of the Treatment Procedures") until month 23 may be applied (maintenance phase).

Experimental/RL group: During the first year of the study the targeted laser photocoagulation will be performed successively up to 4 times (as accessible after resolution of the retinal haemorrhages) along with Ranibizumab injections. It will be restricted to peripheral retinal areas of capillary non-perfusion (detected by ultra-wide field fluorescein angiography [FA]) outside the macula. Control fluorescein angiography (FA) is scheduled at month 3 and 9. If new areas of capillary non-perfusion will be detected, further targeted laser photocoagulation will be performed.

3.2 Requirements at the Trial Sites regarding Personnel and Equipment

3.2.1 Qualification of investigator and medical staff in the study team

The trial will be performed as multicentric study coordinated by [name]. [name] of the Department of Ophthalmology, Justus-Liebig University, Gießen.

Qualification of investigator/deputy and medical staff in the trial team

This chapter defines general requirements for trial staff in the CoRaLa II trial as required by GCP. Trial specific and/or national requirements regarding the qualification of the trial sites and trial staff are specified in the qualification documents used for application to the institutional review board and/or responsible authorities in more detail.

Coordinating Investigator/Principal Investigator

The **coordinating investigator in multicentre trials** and his deputy are licenced to practice medicine, are medical specialists and have at least two years of working experience in the study specific indication. They have theoretical and practical experience in conducting clinical trials.

Principle Investigator/ Investigator

Principal Investigator and Investigators are licenced to practice medicine and are medical specialists in ophthalmology and have experience in the treatment of macular edema due to central retinal vein occlusion.

The Investigator is responsible for selecting and assembling the trial team members (especially the medical staff) according to the requirements of this trial protocol and the specifications in the qualifications documents the sponsor will provide to each trial site. Furthermore, the investigator is responsible for training and supervision of the trial team and providing all necessary information during the course of the trial. This has to be documented accordingly.

All sites will appoint a **blinded BCVA assessor**, who will perform the assessment of BCVA investigation.

